2.3 Study Hypotheses/Research Questions

H1: A greater proportion of participants in the P3 and P3+ arms will have protective levels of TSV-DP/FTC-TP or TAF/FTC-TP (measure of adherence) at months 3 and 6 compared to those in the standard of care arm.

H2: P3+ will cost more to implement than P3, however, we expect the additional P3+ costs to result in meaningful differences in outcomes.

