RCT Eligibility Criteria: 1) ages 16-24; 2) assigned male sex at birth; 3) report sex with men; 4) able to speak and read English; 5) reliable daily access to an Android or iOS smartphone with a data plan; 6) HIV-uninfected (self-report); 7) not currently on PrEP but plan to initiate in the next 7 days and have an active PrEP prescription (prescription confirmed by study staff) OR on PrEP and have an active PrEP prescription (prescription confirmed by study staff); 8) recruited from one of 9 iTech SRV cities (Atlanta, Georgia; Boston, Massachusetts; Bronx, New York; Chapel Hill, North Carolina; Charlotte, North Carolina; Chicago, Illinois; Houston, Texas; Philadelphia, Pennsylvania; Tampa, Florida); 9) willing to adhere to study collection of whole blood specimens. Not eligible: 1) unable to be consented due to active substance use or psychological condition; 2) participated in the field trial; 3) participating in any other experimental PrEP adherence intervention.

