10.2.3 RCT Power Considerations

[figure not shown]
A total of 240 participants will be enrolled at baseline to account for a 20% expected loss to follow-up during the first 3 months of the study leaving an estimated 192 individuals (64 per arm) for analysis. Power was assessed via Monte Carlo simulation. Data were simulated as follows. A single binary baseline variable W was drawn from a Bernoulli (1/2) distribution to represent patient-level characteristics included in the analysis. A binary intervention variable A was drawn from a Bernoulli (2/3) distribution to mimic the 1:1:1 treatment allocation. A binary intermediate variable I_1 was drawn from a Bernoulli (3/4) distribution to mimic participant app utilization. A censoring variable C_1 for the month three visit was drawn from a Bernoulli (1/20) distribution, with the value 1 indicating a participant was lost-to-follow-up before the three-month visit. For uncensored participants, PrEP adherence at month three Y_1 was drawn from a Bernoulli distribution with adherence probability equal to $\text{logit}^{-1}(-1 + \beta_1 A)$. Thus, approximately 27% of participants in the SOC arm were assumed to be adherent at the three-month visit. Note that the parameter β_1 describes the log-odds-ratio of adherence comparing treatment to SOC. Next, we drew L_2 from a Bernoulli (3/4) distribution to mimic participant app utilization after the three month visit, and drew C_2 from a Bernoulli (1/20) distribution, where again a value of 1 indicated a participant was lost-to-follow-up between the three- and six-month visit. For uncensored participants, PrEP adherence at month six Y_2 was drawn from a Bernoulli distribution with adherence probability equal to $\text{logit}^{-1}(-1.5 + \beta_2 A + 1.5 Y_1)$. Thus, approximately 18% of participants in the SOC arm who were not adherent at month three, were adherent at month six, while 50% of participants in the SOC arm who were adherent at month three were again adherent at month six. Note that the parameter β_2 describes the log-odds-ratio of adherence at month six comparing treatment versus control for participants with the same month three adherence.

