of a priori and emergent themes including operational definitions of all codes and sample quotations to illustrate how to apply each code. Two study team members will then use the codebook to independently code the compiled user profiles while a third team member will review these sections of coded data and resolve discrepancies. We will draw a random sample of 20 instances for the coders to begin with and calculate an inter-rater reliability score based on their code assignments. If this score is <95% we will refine the codebook definitions and retrain the coders. Coders will then complete the coding of the remaining instances and we will calculate an inter-rater reliability score. Discrepancies will then be reviewed and resolved by the research team. We will use Dedoose software to assist with theme identification, coding textual data, and describing relationships among codes (via code co-occurrence and memoing functions).⁵⁶ Coding and analytic activities will be discussed during weekly team meetings. Our study team has successfully used all of these methods in past projects with HIV+ YMSM.^{20,57,58}

Cost-comparison between the two intervention study arms: Incremental cost effectiveness ratio (ICER) between the two intervention arms will be defined as $\Delta C / \Delta E$, where ΔC denotes the estimated difference in mean costs of the intervention and ΔE reflects the estimated difference in mean effectiveness between the interventions. ICER will be calculated for outcomes in which the intervention is non-dominated. Cost was measured at the site level. We will calculate ΔC using the mean of costs for each intervention arm. Similarly, we will calculate ΔE using the mean of efficacy measurements for each intervention arm. We will also analyze individual level counseling costs with TMLE if there is substantial variation in time spent on counseling between participants.

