### 4.4 Cost Analysis

Cost was reported at the site-level. To calculate the incremental cost effectiveness ratio we assigned to each participant the average cost per person at their study site and within their treatment arm. We treated this value as if it was the participant's realized cost. This was then used in a complete case analysis comparing the mean cost difference between participants on P3+ vs P3 divided by the mean efficacy difference as measured by the binary TFV measure at 3 months. To create a 95% confidence interval we used the percentile bootstrap method.

Table 7: Super Learner Libraries and variables used for the propensity score and outcome regressions

Model	Outcome	Learner(s)	Baseline Variables 
$\bar{g}_{\Delta Y_j}(a, w_0)$	Self-Reported PrEP use or Exploratory Outcome of Interest Observed	SL.glm	BEO  , BEO*trt
			Age, BEO, On PrEP, Site, Race/Ethnicity
		SL.earth	Age, BEO, on PrEP, Site, Race/Ethnicity, (BEO * On PrEP), (Age*trt)
			Age, BEO, on PrEP, Site, Race/Ethnicity
		HAL	Age, BEO, on PrEP, Site, Race/Ethnicity
		glmnet	Age, BEO, on PrEP, Site, Race/Ethnicity, (BEO * On PrEP), (Age*trt)
$\bar{Q}_k^j(w_0)$	Self-Reported PrEP use or Exploratory Outcome	SL.glm	Age, BEO, on PrEP, Site, Race/Ethnicity, (BEO * On PrEP), (Age*trt)
			Age, BEO, on PrEP, Site, Race/Ethnicity
		SL.earth	Age, BEO, on PrEP, Site, Race/Ethnicity
			Age, BEO, on PrEP, Site, Race/Ethnicity
		HAL	Age, BEO, on PrEP, Site, Race/Ethnicity
		glmnet	Age, BEO, on PrEP, Site, Race/Ethnicity, (BEO * On PrEP), (Age*trt)
Treatment		step	Age, BEO, on PrEP, Site, Race/Ethnicity, (BEO * On PrEP), (Age*trt)

trt -

Treatment

BEO - Exploratory measure at baseline

 Baseline variables to include in the model, in addition to dummy variables for treatment

 If the outcome of interest is available at baseline, it will be controlled for. If not, another variable may be controlled for, if it is predictive for both the EO and missingness.

Table 8: Hypotheses and P-Value Significance Thresholds

Study Objective	Hypothesis	Significance Threshold
Primary	There is no difference between P3/P3+ and SOC in terms of PrEP adherence, as measured by binary FTC-tp.	0.05
	There is no difference between P3/P3+ and SOC in terms of PrEP adherence, as measured by binary TFV-dp.	
Secondary II	There is no difference between P3/P3+ in terms of self-reported weekly PrEP use.	0.025

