### 5.2 Primary and Secondary Analysis Results

The results of these analyses will be presented in four separate tables. The tables will be organized as follows:

- Table 2 will contain results pertaining to the primary objective, see shell table 10.
- Table 3 will contain results pertaining to the secondary objective I, see shell table 11.
- Table 4 will contain results pertaining to the secondary objective II, see shell table 12.
- Table 5 will contain results pertaining to the secondary objective III, see shell table 13. For any significant results, we may also create tables to present comparisons of P3 vs SOC and P3+ vs SOC separately.

Table 10: Estimated difference in proportion of protective PrEP use between treatment group and SOC group as measured by FTC-tp and TFV-dp. (Table 2)

[figure not shown]
P3/P3+ vs. SOC	Estimated Difference	95% CI	p-value
Protective PrEP Level in Blood: TFV-dp			
3 month			
6 month			
Protective PrEP Level in Blood: FTC-tp			
3 month			
6 month			

- Table 6 will contain results pertaining to the cost effectiveness objective.

As mentioned previously, if a formal hypothesis test was not used to compare groups, we will report results descriptively.

In addition to tables we will also visualize results by plotting point estimates and 95% confidence intervals. The plot will contain the average counterfactual outcome on the y-axis, and 3 and 6 months on the x-axis. Each treatment group will have a separate point on the plot. See figure 1 for an example plot.

Figure 1: Example plot for displaying estimates.

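### The percentile bootstrap interval for the P3+ versus P3 cost-effectiveness ratio (SAP 4.4) cannot be read from best to worst once the adherence difference can cross zero

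*SAP*

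**What the plan says.** SAP 4.4 gives each participant the average cost for their site and arm. It continues: "This was then used in a complete case analysis comparing the mean cost difference between participants on P3+ vs P3", divided by the difference in the binary TFV measure at 3 months. Then: "To create a 95% confidence interval we used the percentile bootstrap method". It has no rule for resamples with a zero or negative denominator, and it does not state the resampling unit. SAP 3.3 and the estimand table in SAP 4.1 (Table 6) give the same ratio.

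Protocol 10.3.4 computes the effect difference "using the mean of efficacy measurements for each intervention arm" and adds a condition: "ICER will be calculated for outcomes in which the intervention is non-dominated". It does not say how dominance is judged, and SAP 4.4 does not repeat the condition.

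For reporting, SAP 5.2 says only: "Table 6 will contain results pertaining to the cost effectiveness objective". There is no shell for that table, so separate cost and adherence differences are neither required nor excluded.

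On expectations, H2 in protocol 2.3 has P3+ costing more than P3, and "we expect the additional P3+ costs to result in meaningful differences in outcomes".

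**The concern.** A percentile interval takes its limits from the numerical order of the resampled ratios. That helps a reader only if numerical order is also the order from good to bad. For a cost-effectiveness ratio with a positive cost difference, this holds while the adherence difference stays positive and fails once it crosses zero. Small gains give very large positive ratios and small losses give very large negative ones. The clearest gains and clearest losses both sit nearer zero, with opposite signs.

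A reader of such an interval cannot separate two conclusions: that P3+ may be dominated, and that P3+ may be effective but expensive per gain. A large negative limit could even be taken for a saving. This interval is the only uncertainty measure that SAP 4.4 plans for a named study objective, and H2 depends on that objective.

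**Working it through.** **1. The plan's own sample size.** Protocol 10.2.3 enrols 240 and expects 20% loss by month 3: 240 × 0.80 = 192, and 192 / 3 = 64 per arm. This reproduces "leaving an estimated 192 individuals (64 per arm) for analysis". SAP 6.2 expects high DBS missingness, so complete cases may be fewer.

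**2. Loss of order.** Take a cost difference ΔC of 100 (assumed; no amounts are given) and compute ΔC/ΔE:

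| ΔE (P3+ minus P3) | Ratio |
|---|---|
| +0.10 | 1,000 |
| +0.01 | 10,000 |
| −0.01 | −10,000 |
| −0.10 | −1,000 |

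Desirability falls steadily down the table. The ratio rises, jumps to a large negative value, then rises again.

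**3. Precision of the denominator.** SE(ΔE) = √[p₁(1−p₁)/n₁ + p₂(1−p₂)/n₂]. With 64 per arm, P3 at 41% (27% SOC plus the 14-point pooled effect in protocol 10.2.3; an assumption for P3) and P3+ at 51%: √(0.2419/64 + 0.2499/64) = 0.088, so the 95% half-width is 1.96 × 0.088 = 17 points. The share of the sampling distribution below zero is Φ(−0.10/0.088) = 13%. At gains of 5, 14 and 20 points the shares are 28%, 5.5% and 1.0%.

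**4. How often the limits change sign.** The documents give no P3 rate. RCT criterion 7 in protocol 3.2 admits people about to start PrEP "OR on PrEP and have an active PrEP prescription (prescription confirmed by study staff", so P3 rates from 27% to 80% were tried. Simulation: 64 vs 64 and 61 vs 66 complete cases, at least 2,000 trials per setting with 1,000 resamples each. Participants were resampled within arm and zero denominators dropped. The cost difference was 100, either fixed or built from site-by-arm averages. Share of trials with lower limit < 0 < upper limit:

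| P3 rate | 5 points | 10 points | 14 points | 20 points |
|---|---|---|---|---|
| 27-50% | 88-91% | 74-79% | 56-64% | 30-38% |
| 60% | 90-91% | 74-77% | 54-59% | 26-29% |
| 70% | 87-90% | 71% | about half | 14-16% |
| 80% | 86-89% | 56-66% | 25-31% | not possible |

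Repeat runs moved single entries by about 3 points at most. With 48 vs 48 or 46 vs 50 and P3 at 27-50%, the shares were 89-91%, 77-83%, 64-69% and 42-48%. Coverage of the true ratio at about 64 per arm was 94-98%.

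**5. Worked examples (ΔC fixed at 100).**

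- P3 25/61, P3+ 34/66: ΔE = 0.515 − 0.410 = 0.105, ratio 100/0.1053 = 950. About 12% of resamples have ΔE < 0. The limits are about −12,200 and +8,400. Turned back into adherence differences, they are 100/−12,200 = −0.8 points and 100/8,400 = +1.2 points. Both limits therefore come from near-null resamples. The adherence difference itself reads plainly: 11 points (−7 to 28).
- P3 43/61, P3+ 54/66: ΔE = 0.818 − 0.705 = 0.113, ratio 883, limits about −6,000 and +6,700, adherence difference 11 points (−3 to 26).

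**6. A readable alternative on the first example.** Net benefit λΔE − ΔC at λ = 500, 1,000 and 2,000 is −47 (−134 to 39), 5 (−168 to 178) and 111 (−235 to 456). Simulated coverage of net-benefit intervals was 93-96%.

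**The case against.** **The protocol limits the ratio to non-dominated outcomes.** It does, but that condition decides which outcomes get a ratio. It does not say how dominance is judged and does not deal with individual resamples. If it is applied to the point estimate, about 53-76% of trials with a positive estimate still have mixed-sign limits at a true gain of 10 points.

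**Readers will see the adherence results elsewhere.** This stands in part. SAP Table 11 reports P3 and P3+ each against SOC with 95% intervals at 3 months, and SAP 5.2 plans a plot of each group's estimate. A reader can see roughly where P3+ lies relative to P3. Neither display gives an interval for P3+ minus P3, and both rest on TMLE rather than on the complete cases used in the ratio.

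**Coverage is adequate.** Agreed. A reader might infer that the interval is invalid because it misses the true ratio; the simulations do not support that.

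**A large effect removes the problem.** Also true. With 64 per arm, less than 2.5% of the distribution lies below zero once the gain reaches about 16.5 to 17.5 points (P3 27-56%). No P3+ versus P3 effect of that size, or of any size, is assumed in the documents.

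**The cost analysis ignores TMLE.** A reader might infer that the protocol leaves costs wholly on simple arm means. It does not: protocol 10.3.4 also plans TMLE for individual counseling costs if counseling time varies substantially.

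**Conclusion.** The concern holds as a matter of interpretation. Following SAP 4.4 as written can give limits that cannot be read from best to worst, because P3+ is expected to cost more and the denominator is imprecise. At about 64 per arm, mixed-sign limits occur in more than half of simulated trials at gains of 5 or 10 points for every P3 rate tried. At 14 points the outcome depends on the P3 rate: 56-64% at 27-50%, about half at 70%, and 25-31% at 80%. At 20 points it is the minority case, about 14-38% for P3 rates of 27-70%.

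These frequencies rest on assumed P3 rates, assumed gains, a positive cost difference, resampling within arm and dropping zero denominators. The loss of order in step 2 needs only the positive cost difference.

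Two stronger readings are not supported. The interval is not always unreadable: when the resampled adherence differences stay clear of zero, it can be used. The point also does not reach the primary or secondary efficacy conclusions, which do not use the ratio. It is worth acting on because the remedy is cheap, but it is a modest point.

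**What to change.** In SAP 4.4:

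1. Report the cost difference and the P3+ minus P3 difference in protective TFV, each with its own 95% CI, on the complete cases used for the ratio.
2. Show the bootstrap cost-effectiveness plane with the share of resamples in each quadrant, and incremental net benefit (λΔE − ΔC) with its CI over a stated range of λ.
3. When the adherence-difference interval includes zero, do not report the ratio's percentile limits as a CI. Give the ratio as a point estimate only, and only if P3+ is both costlier and more effective, and state that its interval is not interpretable.

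The cost is SAP wording and a short program on existing data. More numbers are reported, and a λ range must be chosen because the documents give none. The revision history dates the addition of SAP 4.4 to 13 July 2022, after the analysis completion date of 20 April 2022 in SAP 6.1. The added output and the choice of λ must therefore be labelled post hoc.

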## 5 Reporting Results

### 5.1 Initial Descriptive Statistics and Data Exploration

Before conducting a formal causal analysis using the g-formula and assumptions described above, we will first use descriptive statistics to describe the study cohort and understand our study variables. Table 1, will include patient baseline characteristics (including demographic, social, baseline sexual risk variables, PrEP use, and study site) for the entire cohort, stratified by treatment group (see table 9 for a shell table).

To visualize differences in study outcomes by treatment group for both the primary objective and secondary objectives I and II, we will plot line graphs, with crude average trend lines for each treatment group. For continuous outcomes individual trend lines may also be plotted on these graphs.

### 5.2 Primary and Secondary Analysis Results

The results of these analyses will be presented in four separate tables. The tables will be organized as follows:

- Table 2 will contain results pertaining to the primary objective, see shell table 10.
- Table 3 will contain results pertaining to the secondary objective I, see shell table 11.
- Table 4 will contain results pertaining to the secondary objective II, see shell table 12.
- Table 5 will contain results pertaining to the secondary objective III, see shell table 13. For any significant results, we may also create tables to present comparisons of P3 vs SOC and P3+ vs SOC separately.

Table 10: Estimated difference in proportion of protective PrEP use between treatment group and SOC group as measured by FTC-tp and TFV-dp. (Table 2)

[figure not shown]
P3/P3+ vs. SOC	Estimated Difference	95% CI	p-value
Protective PrEP Level in Blood: TFV-dp			
3 month			
6 month			
Protective PrEP Level in Blood: FTC-tp			
3 month			
6 month			

- Table 6 will contain results pertaining to the cost effectiveness objective.

As mentioned previously, if a formal hypothesis test was not used to compare groups, we will report results descriptively.

In addition to tables we will also visualize results by plotting point estimates and 95% confidence intervals. The plot will contain the average counterfactual outcome on the y-axis, and 3 and 6 months on the x-axis. Each treatment group will have a separate point on the plot. See figure 1 for an example plot.

Figure 1: Example plot for displaying estimates.

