### 3.2 Secondary Study Objectives

As detailed in the study protocol, the secondary objectives of this analysis are as follows:

1. Replicate the primary objectives with P3 and P3+ considered separately against the SOC group (i.e. P3 vs. SOC and P3+ vs SOC).
2. Analyze the effect of the intervention on self-reported weekly PrEP use and self-reported monthly PrEP use.
3. Analyze the effect of intervention on a panel of self-reported outcomes which include, PrEP retention and persistence, PrEP clinical care, sexual risk, and incident sexually transmitted infection (STI).

The outcomes for secondary objective one are the same as the primary outcome and are listed in table 4. Table 5 lists outcomes for secondary objectives two and three. These outcomes will be assessed at both the 3 month time point and the 6 month time point.

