### 4.1 Notation and Causal Estimands

The following notation will be used to denote study data:

- $A$ : randomized treatment assignment at baseline
- $Y_j$ : outcome of interest at the  $j$ th time point
- $W_0$ : patient baseline covariates
- $\Delta_{Yj}$  whether or not  $Y_j$  was measured for the patient (1 = observed, 0 = missing)

The subscript  $j$  will take on values 0, 1, 2, to denote data collected at baseline, 3 months and 6 months, respectively. We assume that the observed data may be represented sequentially for the three month outcome as  $O_1 = (W_0, A, \Delta_{Y,1}, \Delta Y_1)$  and for the six month outcome as  $O_2 = (W_0, A, \Delta_{Y,2}, \Delta Y_2)$ .

In order to define our causal estimands of interest, we use counterfactual notation. Counterfactual notation describes the outcome a participant would have under a specified intervention (even if that intervention was not observed for the patient). We denote this outcome as  $Y(a)$  to represent the outcome under treatment  $A = a$ . Our estimands of interest generally take the form  $E[Y(1) - Y(0)]$  which is the expected difference in the average outcome if everyone in the population took treatment one versus treatment zero. We use the following notation to describe the assigned treatments:  $(a_1)$  control,  $(a_2)$  P3 and P3+,  $(a_{2a})$  P3, and  $(a_{2b})$  P3+. Table 6 outlines the estimands of interest for each study objective. Note that since a patient

Table 6: Estimands of Interest.

Study Objective	Estimand a	Comparison	Outcome(s)
Primary	$P[Y(a_2)] - P[Y(a_1)]$	Average effect of P3/P3+, compared to SOC	Protective levels of TFV-dp and FTC-tp in DBS
Secondary I	$P[Y(a_{2a})] - P[Y(a_1)]$	Average effect of P3 compared to SOC	Same as primary
	$P[Y(a_{2b})] - P[Y(a_1)]$	Average effect of P3+ compared to SOC	
Secondary II	$P[Y(a_2)] - P[Y(a_1)]$	Average effect of P3/P3+ compared to SOC	Self-reported weekly PrEP use Self-reported monthly PrEP use
Secondary III	$P[Y(a_2)] - P[Y(a_1)]$	Average effect of P3/P3+ compared to SOC	Panel of self-reported outcomes
Cost	$\frac{E[C(a_{2b}) - C(a_{2a})]}{E[Y(a_{2b}) - Y(a_{2a})]}$	Ratio of expected cost difference to expected efficacy difference between P3+ and P3	C will be calculated cost and Y will be the outcome of interest for assessing treatment efficacy

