### 4.3 Hypothesis Tests and Multiple Testing Adjustment

Table 8 lists the hypotheses to be tested for each study objective. Each hypothesis comparing P3/P3+ to SOC will be tested at both 3 and 6 months, separately. For comparisons of P3 vs SOC and P3+ vs SOC, we will report the comparisons in a descriptive manner as opposed to conducting additional hypothesis tests (i.e. Secondary objectives I, II, and III).

Table 8 lists the p-value adjustment for each hypothesis test. For the primary objective no adjustment is done. For secondary objective II, a Bonferroni Correction will be applied to adjust for multiple testing and to maintain a nominal alpha level of approximately 0.05 within the objective. Due to the exploratory nature of secondary objective III, we will use a Benjamini-Hochberg adjustment, which controls the false discovery rate (FDR). We will use 0.20 as the desired FDR, which is the proportion of rejected null hypotheses that are actually true (See Glickman, 2014 for more information).

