## 6 General Considerations and Statistical Issues

### 6.1 Timeline

1. Data Available: February 24, 2022
2. Analysis Done: April 20, 2022
3. Manuscript Complete: TBD

Table 11: Estimated difference in proportion of protective PrEP use between treatment groups and SOC group, where P3 and P3+ are considered separately (table 3)

P3 vs. SOC	Estimated Difference	95% CI
Protective PrEP Level in Blood: TFV-dp		
3 months		
6 months		
P3+ vs. SOC	Estimated Difference	95% CI
Protective PrEP Level in Blood: TFV-dp		
3 months		
6 months		
P3 vs. SOC	Estimated Difference	95% CI
Protective PrEP Level in Blood: FTC-tp		
3 months		
6 months		
P3+ vs. SOC	Estimated Difference	95% CI
Protective PrEP Level in Blood: FTC-tp		
3 months		
6 months		

Table 12: Estimated difference in self-reported PrEP use between treatment groups and SOC group.

P3/P3+ vs SOC	Estimated Ratio	95% CI	p-value
Self-reported Weekly PrEP Use			
3 months			
6 months			
Self-reported Monthly PrEP Use			
3 months			
6 months			
P3 vs SOC	Estimated Ratio	95% CI	
Self-reported Weekly PrEP Use			
3 months			
6 months			
Self-reported Monthly PrEP Use			
3 months			
6 months			
P3+ vs SOC	Estimated Ratio	95% CI	
Self-reported Weekly PrEP Use			
3 months			
6 months			
Self-reported Monthly PrEP Use			
3 months			
6 months			

Table 13: Estimated difference in proportions (or mean outcomes) between treatment group and SOC group for self-reported exploratory outcomes (table 5)

P3/P3+ vs SOC	Estimated Difference	95% CI	p-value
Outcome 1			
3 months			
6 months			
Outcome 2			
3 months			
6 months			

Table 14: Frequency of Missing Data, in entire cohort and by treatment group, reported as count (%). (table 7)

Variable	Total (N= )	P3 (N= )	P3+ (N= )	SOC (N= )
Baseline data				
Baseline Variables				
3 month data				
TFV-dp				
FTC-tp				
Outcome 1				
...				
Outcome p				
6 month data				
TFV-dp				
FTC-tp				
Outcome 1				
...				
Outcome p				

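### SAP 5.2 makes optional P3 vs SOC and P3+ vs SOC tables for Secondary III depend on significance, which conflicts with SAP 4.3 and would select inflated arm-level estimates

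*SAP*

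**What the plan says.** SAP 5.2 assigns one results table to each objective. For the third it says "Table 5 will contain results pertaining to the secondary objective III, see shell table 13", with no condition, and then adds: "For any significant results, we may also create tables to present comparisons of P3 vs SOC and P3+ vs SOC separately". The only formal tests in Secondary III are the pooled P3/P3+ vs SOC tests, so these are the results whose significance counts. SAP 4.3 sets the rule: Benjamini-Hochberg, with "We will use 0.20 as the desired FDR".

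SAP 4.3 also deals with the separate-arm comparisons directly: "we will report the comparisons in a descriptive manner as opposed to conducting additional hypothesis tests (i.e. Secondary objectives I, II, and III". It attaches no significance condition.

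The shell tables differ by objective. Tables 11 and 12 (objectives I and II) have P3 vs SOC and P3+ vs SOC blocks with estimates and CIs whatever the result. Table 13 (objective III) has P3/P3+ vs SOC rows only. SAP Table 6 defines the Secondary III estimand as the pooled contrast. SAP 5.2 also plans plots of point estimates with 95% CIs, in which "Each treatment group will have a separate point on the plot", but does not say which outcomes are plotted.

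**The concern.** Two sections of the SAP give different instructions for the same comparisons. An analyst following 4.3 reports P3 vs SOC and P3+ vs SOC for every Secondary III outcome. An analyst following 5.2 and shell table 13 reports them, if at all, only where the pooled result was significant. The word *may* adds a further choice made after the results are known.

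The 5.2 route has a statistical cost. The pooled estimate and the arm-level estimates come from the same participants and share the SOC arm. Showing arm-level estimates only after a significant pooled result selects the more extreme draws, and their ordinary 95% CIs do not allow for that. Readers of the arm-level tables would see effects on retention, persistence, sexual risk or STI that look larger than they are, with the less extreme ones missing from that display. Protocol 2.3 (H2) expects the added cost of P3+ to bring meaningful differences in outcomes, so arm-level results are likely to be read closely.

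**Working it through.** **Inputs from the documents**
- Evaluable sample (Protocol 10.2.3): 240 × (1 − 0.20) = 192, and 192 / 3 = 64 per arm. This reproduces the stated figure.
- SOC rate: the inverse logit of −1 is 0.269, the protocol's 27%. That is the adherence assumption; the documents give no rate for Secondary III outcomes, so it is borrowed.
- Outcomes: the SAP's outcome table (Table 5) lists three STIs, persistence, retention and two sexual-risk counts, so 7. SAP 3.2 says "These outcomes will be assessed at both the 3 month time point and the 6 month time point", giving up to 7 × 2 = 14 tests. The SAP does not define the Benjamini-Hochberg family, so 14, 7 and 5 tests were tried.
- Selection rule: Benjamini-Hochberg at 0.20. The threshold for the k-th smallest of m p-values is 0.20 × k / m. A lone rejection needs p ≤ 0.20 / 14 = 0.014 with 14 tests, or p ≤ 0.20 / 5 = 0.04 with 5.

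**Why selection carries over to the arms**

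Let each arm's estimated proportion have variance v.
- Pooled contrast (average of P3 and P3+, minus SOC): variance v/2 + v = 1.5v.
- Its covariance with P3 minus SOC: v/2 + v = 1.5v.
- Regression slope of P3 vs SOC on the pooled contrast: 1.5v / 1.5v = 1.

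With equal variances, any inflation of the pooled estimate through selection passes in full to each arm-vs-SOC estimate.

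For P3+ minus P3, the covariance with the pooled contrast is (variance of P3+ − variance of P3) / 2. This is zero when the variances are equal. With unequal rates, say 0.27 in SOC and P3 and 0.42 in P3+:
- The variances are 0.27 × 0.73 / 64 = 0.00308 and 0.42 × 0.58 / 64 = 0.00381.
- The covariance is (0.00381 − 0.00308) / 2 = 0.00036.
- The pooled variance is 0.00308 + (0.00308 + 0.00381) / 4 = 0.00480.
- The slope is 0.00036 / 0.00480, or about 0.08.

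A pooled inflation of about 0.10 would therefore move P3+ minus P3 by only about 0.008.

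**Simulation** (40,000 replicates; 64 per arm; independent binary outcomes; pooled Wald tests put through Benjamini-Hochberg at 0.20; two outcomes with a true effect equal in both arms, the rest null). The table gives the mean P3 vs SOC estimate among outcomes whose pooled test was rejected, with coverage of the ordinary 95% CI in brackets.

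| True difference | 14 tests | 7 tests | 5 tests |
|---|---|---|---|
| 0.05 | 0.170 (68%) | 0.156 (76%) | 0.148 (79%) |
| 0.10 | 0.191 (87%) | 0.178 (90%) | 0.170 (92%) |
| 0.14 | 0.204 (93%) | 0.192 (95%) | 0.187 (95%) |
| 0.20 | 0.231 (96%) | 0.223 (96%) | 0.219 (96%) |

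- **No selection.** When every outcome is reported, the mean estimate equals the true value and coverage is about 94% to 95%.
- **All outcomes null.** At least one outcome is selected in 22% to 24% of trials. The mean absolute P3 vs SOC estimate among those selected is 0.15 to 0.17, against 0.06 without selection.
- **P3 truly 0, P3+ truly 0.15, 14 tests.** The P3 vs SOC estimate averages 0.10 when selected.

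**The case against.** The strongest reply is that no planned estimand is withheld. The Secondary III estimand is the pooled contrast, in SAP Table 6 and in Protocol 10.3.4, and it is tabulated for every outcome whatever its p-value. The separate-arm tables are an optional extra on outcomes the SAP itself treats as exploratory, and 4.3 already promises descriptive reporting. This stands, and it makes the point minor. It does not remove the conflict: 5.2 and shell table 13 still lead to a different report from 4.3.

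A reader might infer that null or adverse arm-level results will never appear, and that only favourable ones will. The documents do not support this. The sentence in 5.2 is permissive, 4.3 points the other way, and the planned plots may show each arm. The tests are two-sided, so a significantly adverse pooled result would open the same tables. The selection is towards extreme results, not favourable ones.

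A reader might also infer that the comparison of P3 with P3+ is distorted. The covariance argument shows that it is nearly untouched; the inflation lies in each arm against SOC.

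Finally, the size rests on borrowed inputs. That is fair. The 27% rate is an adherence figure, the outcomes will be correlated, and the two sexual-risk outcomes are counts, so a difference in proportions does not describe them.

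**Conclusion.** The concern holds as a minor reporting point. SAP 5.2 attaches a significance condition, and discretion, to arm-level Secondary III tables that 4.3 says will be reported without condition. Shell tables 11 and 12 show that objectives I and II are handled without it.

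If 5.2 is followed, arm-vs-SOC estimates are biased away from zero in the direction that was significant. Under the illustrative assumptions a true 0.05 appears roughly three times too large (0.148 / 0.05 = 3.0 to 0.170 / 0.05 = 3.4). At 0.20 the excess is only 0.02 to 0.03. The direction follows from the shared data; the size depends on the assumed event rate, independence, binary outcomes and family size. The primary analysis, the pooled Secondary III results and, to a close approximation, the P3+ vs P3 contrast are not affected.

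**What to change.** Delete the significance condition from SAP 5.2 and align the section with 4.3. Add P3 vs SOC and P3+ vs SOC rows to shell table 13, or to a supplementary table, for every Secondary III outcome at 3 and 6 months. Give the estimated difference and 95% CI and no p-value, since 4.3 rules out further tests. Keep shell table 13's difference column: shell table 12 is headed as a ratio, whereas Secondary III effects are differences in proportions or means.

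The cost is one longer descriptive table. The outcome regressions in SAP 4.2 already carry a dummy variable for each intervention arm, and SAP 6.1 lists the manuscript date as still to be determined. If the team does not want the extra rows, stating that no arm-level Secondary III results will be reported would also remove the result-dependent choice, but 4.3 would then have to be changed to match.
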